### 9.5.2.2 Description of Procedures/Assessments Schedule

#### SCREENING PHASE ASSESSMENT SCHEDULE

##### SCREENING PERIOD ASSESSMENTS

###### **Screening Visit (Visit 1, Day -28 to Day -7)**

Written informed consent is obtained from the patients (if possible) and from legal guardian. The caregiver should separately provide written informed consent for his/her own participation in the study. Once informed consent has been obtained, the following procedures and evaluations will be performed:

- Subject medical history; subject and caregiver demographic information
- Record prior and concomitant medication use over the past 12-week.
- Diagnosis (NINDS-AIREN): Hachinski Ischemia Scale, Neurological Examination, Cranial MRI or CT, CDR
- MMSE (Mini-Mental State Examination)
- Vital signs (systolic and diastolic BP in supine and sitting position, pulse), and weight
- 12-lead ECG
- Blood and urine samples for clinical laboratory assessments and pregnancy testing (serum, only females of childbearing potential)
- Any AEs to be collected from the time of consent
- Review of inclusion/exclusion criteria for subject and caregiver
- Schedule Baseline Visit 2

#### BASELINE ASSESSMENTS

###### **Baseline Visit (Visit 2, Week 0)**

The results of all screening assessments and evaluations must be completed and reviewed by the PI before the subject's arrival for the visit. Only those subjects who continue to meet all of the inclusion and none of the exclusion criteria are eligible to continue in the study. This is intended to minimize variability in subject and caregiver response. It is further recommended (whenever possible) that subjects be evaluated at approximately the same time of the day (e.g., morning or afternoon) at each subsequent visit.

The following procedures and evaluations will be performed:

- Record all prior and concomitant medication use.
- MMSE (Mini-Mental State Examination)
- Vital signs (systolic and diastolic BP in supine and sitting position, pulse), and weight
- Collect urine samples for pregnancy test (urine, only females of childbearing potential)
- Record any AEs
- Review of inclusion/exclusion criteria for subject and caregiver
- ADAS-cog, executive function test
- CIBIS

- Randomization (Randomly assigned as 1:1 ratio by IWRS system)
- Dispense study medication.
- Schedule Visit3

**Caregiver's Responsibilities:** Prior to leaving the study site, the caregiver will receive an appointment schedule for the next visit and study medication containing drug supply sufficient for the period prior to the next clinic visit. It is the caregiver's responsibility to help to ensure that the medication is stored safely in the home, to assist in patient compliance with taking their medication and making clinic visits and to provide the investigator with information for the evaluation of psychometric/neurological functions.

## **DOUBLE-BLIND PHASE ASSESSMENT SCHEDULE**

### **TITRATION PERIOD ASSESSMENTS**

#### **Visits 3 (Week 4, Day 28-35)**

The following procedures and evaluations will be performed:

- Record all concomitant medication use
- Collect unused study medication and record compliance
- MMSE
- ADAS-cog
- CIBIC
- Vital signs (sitting systolic and diastolic BP, pulse) and weight
- 12-Lead ECG
- Record any AEs
- Dispense study medication.
- Schedule Visit 4

### **MAINTENANCE PERIOD ASSESSMENTS**

#### **Visits 4 (Week6, Day 35-49)**

The following procedures and evaluations will be performed:

- Record all concomitant medication use
- Collect unused study medication and record compliance
- Vital signs (sitting systolic and diastolic BP, pulse) and weight
- 12-Lead ECG
- Blood and urine samples for clinical laboratory determinations (including urine pregnancy test for females of childbearing potential)
- Record any AEs
- Dispense study medication.
- Schedule Visit 5

**Visit 5 (Week12, Day 77-91)**

The following procedures and evaluations will be performed:

- Record all concomitant medication use
- Collect unused study medication and record compliance
- MMSE
- ADAS-cog, executive function test
- CIBIC
- Vital signs (sitting systolic and diastolic BP, pulse) and weight
- 12-lead ECG
- Blood and urine samples for clinical laboratory determinations (including urine pregnancy test for all females of childbearing age)
- Record any AEs
- Dispense study medication.
- Schedule Visit 6

**Visit 6 (Week 18, Day 119-133)**

The following procedures and evaluations will be performed:

- Record all concomitant medication use
- Collect unused study medication and record compliance
- MMSE
- ADAS-cog
- Vital signs (sitting systolic and diastolic BP, pulse) and weight
- 12-lead ECG
- Blood and urine samples for clinical laboratory determinations (including urine pregnancy test for all females of childbearing age)
- Record any AEs
- Dispense study medication
- Schedule Visit 7

**Visit 7 (Week 24, Day 161-168) or Early discontinuation**

The following procedures and evaluations will be performed:

- Record all concomitant medication use
- Collect unused study medication and record compliance
- MMSE
- ADAS-cog, executive function test
- CIBIC
- Vital signs (sitting systolic and diastolic BP, pulse) and weight
- 12-lead ECG
- Blood and urine samples for clinical laboratory determinations (including urine pregnancy test for all females of childbearing age)

- Record any AEs

## **OPEN-LABEL EXTENSION PHASE ASSESSMENT SCHEDULE**

### **BASELINE VISIT**

#### **Visit 7 (OLE Week 0, same as Week 24 of DB phase)**

The following procedures and evaluations will be performed:

- Obtain written informed consent
- Dispense study medication.
- Schedule Visit 8 if the subjects will be enrolled in the open-label extension phase
- 

### **TITRATION PERIOD ASSESSMENTS**

#### **Visit 8 (OLE Week 6, Day 28-42)**

The following procedures and evaluations will be performed:

- Record all concomitant medication use
- Collect unused study medication and record compliance
- MMSE
- Vital signs (sitting systolic and diastolic BP, pulse) and weight
- 12-lead ECG
- Blood and urine samples for clinical laboratory determinations (including urine pregnancy test for all females of childbearing age)
- Record any AEs
- Dispense study medication.
- Schedule Visit 9

The dose can be increased to 10 mg/day after confirmation of clinical response at Visit 8 (Week 6).

### **MAINTENANCE (FLEXIBLE DOSE) PERIOD ASSESSMENTS**

#### **Visit 9 (OLE Week 12, Day 77-91)**

The following procedures and evaluations will be performed:

- Record all concomitant medication use
- Collect unused study medication and record compliance
- MMSE
- Vital signs (sitting systolic and diastolic BP, pulse) and weight
- 12-lead ECG
- Blood and urine samples for clinical laboratory determinations (including urine pregnancy test for all females of childbearing age)
- Record any AEs
- Dispense study medication.

- Schedule Visit 10

**Visit 10 (OLE Week 24, Day 161-175) and Early discontinuation**

The following procedures and evaluations will be performed:

- Record all concomitant medication use
- Retrieve unused study medication and record compliance
- MMSE
- Vital signs (sitting systolic and diastolic BP, pulse) and weight
- 12-lead ECG
- Blood and urine samples for clinical laboratory determinations (including urine pregnancy test for all females of childbearing age)
- Record any AEs

**9.5.3 Appropriate ness of Measurements**

All clinical assessments are standard measurements commonly used in studies of dementia associated with cardiovascular disease.

The safety assessments to be performed in this study, including hematology analysis, blood chemistry test, urinalysis, radiologic studies and assessments of AEs, are standard evaluations to ensure subjects safety.

**9.5.4 Reporting of Serious Adverse Events, Pregnancy, and Other Events of Interest****9.5.4.1 Reporting of Serious Adverse Events**

**All SERIOUS ADVERSE EVENTS, regardless of their relationship to study treatment, must be reported on a completed SAE form by email or fax as soon as possible but no later than 1 business day from the date the investigator becomes aware of the event.**

Serious adverse events, regardless of causality assessment, must be collected through the last visit and for 30 days after the subject's last dose. All SAEs must be followed to resolution or, if resolution is unlikely, to stabilization. Any SAE judged by the investigator to be related to the study treatment should be reported to the sponsor regardless of the length of time that has passed since study completion.

**Deaths and life-threatening events should be reported immediately by telephone. The immediate report should be followed up within 1 business day by emailing or faxing the completed SAE form.**

The detailed contact information for reporting of SAEs is provided in the Investigator Study File.

**For urgent safety issues call: Designated CRO (C&R Research) contact number**

**For urgent safety issues, please ensure all appropriate medical care is administered to the subject and contact the appropriate study team member listed in the Investigator Study File.**

It is very important that the SAE report form be filled out as completely as possible at the time of the initial report. This includes the investigator's assessment of causality.

Any follow-up information received on SAEs should be forwarded within 1 business day of its receipt. If the follow-up information changes the investigator's assessment of causality, this should also be noted on the follow-up SAE form.

Preliminary SAE reports should be followed as soon as possible by detailed descriptions including copies of hospital case reports, autopsy reports, and other documents requested by the sponsor.

#### 9.5.4.2 Reporting of Pregnancy and Exposure to Study Drug through Breastfeeding

Any pregnancy in which the estimated date of conception is either before the last visit or within 30 days of last study treatment or any exposure to study drug through breastfeeding during study treatment or within 30 days of last study treatment must be reported

If an adverse outcome of a pregnancy is suspected to be related to study drug exposure, this should be reported regardless of the length of time that has passed since the exposure to study treatment.

A congenital anomaly, death during perinatal period, an induced abortion, or a spontaneous abortion are considered to be an SAE and should be reported in the same time frame and in the same format as all other SAEs (see Reporting of Serious Adverse Events [Section 9.5.4.1]).

Pregnancies or exposure to study drug through breastfeeding must be reported by fax or email as soon as possible but no later than 1 business day from the date the investigator becomes aware of the pregnancy. The contact information for the reporting of pregnancies and exposure to study drug through breastfeeding is provided in the Investigator Study File. The Pregnancy Report Form must be used for reporting. All pregnancies must be followed to outcome. The outcome of the pregnancy must be reported as soon as possible but no later than 1 business day from the date the investigator becomes aware of the outcome.

A subject who becomes pregnant must be withdrawn from the study.

#### 9.5.4.3 Reporting of Other Events of Interest

##### **REPORTING OF ADVERSE EVENTS ASSOCIATED WITH STUDY DRUG OVERDOSE, MISUSE, ABUSE, OR MEDICATION ERROR**

Adverse events associated with study drug overdose, misuse, abuse, and medication error refer to AEs associated with uses of the study drug outside of that specified by the protocol. Overdose, misuse, abuse, and medication error are defined as follows:

Overdose	Accidental or intentional use of the study drug in an amount higher than the protocol-defined dose
Misuse	Intentional and inappropriate use of study drug not in accordance with the prescribed or authorized dose, route of administration, or indication(s) or use of prescription-only study drug without a prescription

Abuse	Sporadic or persistent intentional excessive use of study drug accompanied by harmful physical or psychological effects
Medication error	Any unintentional event that causes or leads to inappropriate study drug use or subject harm while the study drug is in the control of site personnel or the subject.

All AEs associated with an overdose should be captured on the Adverse Event CRF. Adverse events associated with overdose, misuse, abuse, or medication error should be reported using the procedures detailed in Reporting of Serious Adverse Events (Section 9.5.4.1) even if the AEs do not meet serious criteria. Abuse is always to be captured as an AE. If the AE associated with an overdose, misuse, abuse, or medication error does not meet serious criteria, it must still be reported using the SAE form and in an expedited manner but should be noted as nonserious on the SAE form and the Adverse Event CRF.

#### 9.5.4.4 Expedited Reporting

The sponsor must inform investigators and regulatory authorities of reportable events, in compliance with applicable regulatory requirements, on an expedited basis (i.e., within specific time frames). For this reason, it is imperative that sites provide complete SAE information in the manner described above.

#### 9.5.4.5 Breaking the Blind

In the case of a medical emergency where the appropriate treatment of the subject requires knowledge of the study treatment given, the investigator may break the randomization code for an individual subject. In all such cases, the AE necessitating the emergency blind break will be handled as an SAE in accordance with the procedures indicated above. Any broken code will be clearly justified and documented. The medical monitor must be notified immediately of the blind break.

#### 9.5.4.6 Regulatory Reporting of Adverse Events

Adverse events will be reported by the sponsor or a third party acting on behalf of the sponsor to regulatory authorities in compliance with local and regional law and established guidance. The format of these reports will be dictated by the local and regional requirements.

### 9.5.5 Completion/Discontinuation of Subjects

A subject may elect to discontinue the study at any time for any reason. All subjects who discontinue the study are to complete the study's early discontinuation procedures indicated in the Schedule of Procedures/Assessments (Table 2 and Table 3).

The investigator will promptly explain to the subject involved that the study will be discontinued for that subject and provide appropriate medical treatment and other necessary measures for the subject. A subject who has ceased to return for visits will be followed up by mail, phone, or

other means to gather information such as the reason for failure to return, the status of treatment compliance, the presence or absence of AEs, and clinical courses of signs and symptoms. This information will be recorded in the CRF.

Subjects who discontinue early from the study will be discontinued for one of these primary reasons: AE(s), lost to follow-up, subject choice, progression of disease, protocol violation, pregnancy, study terminated by sponsor, or other. In addition to the primary reason, the subject may indicate one or more of secondary reasons for discontinuation. Study disposition information will be collected on the appropriate CRF.

#### **9.5.6 Abuse or Diversion of Study Drug**

Not applicable.

#### **9.5.7 Confirmation of Medical Care by Another Physician**

Not applicable.

### **9.6 DATA QUALITY ASSURANCE**

This study will be organized, performed, and reported in compliance with the protocol, SOPs, working practice documents, and applicable regulations and guidelines. Site audits will be made periodically by the sponsor's or the CRO's qualified compliance auditing team, which is an independent function from the study team responsible for conduct of the study.

#### **9.6.1 Data Collection**

Data required by the protocol will be collected on the CRFs and entered into a validated data management system that is compliant with all regulatory requirements. As defined by ICH guidelines, the CRF is a printed, optical, or electronic document designed to record all of the protocol-required information to be reported to the sponsor on each study subject.

Data collection on the CRF must follow the instructions described in the CRF Completion Guidelines. The investigator has ultimate responsibility for the collection and reporting of all clinical data entered on the CRF. Completed, original CRFs are the sole property of Eisai and should not be made available in any form to third parties without written permission from Eisai, except for authorized representatives of Eisai or appropriate regulatory authorities.

#### **9.6.2 Clinical Data Management**

All software applications used in the collection of data will be properly validated following standard computer system validation that is compliant with all regulatory requirements. All data, both CRF and external data (e.g., laboratory data), will be entered into a clinical system.

### **9.7 STATISTICAL METHODS**

All statistical analyses will be performed by the sponsor or designee. Statistical analyses for DB phase will be performed after a snapshot of the database is obtained and released for unblinding.

Statistical analyses for OLE phase will be performed after the study is completed and the database is locked.

### **9.7.1 Statistical and Analytical Plans**

The statistical analyses of core study data (DB phase) are described in this section. Further details of the analytical plan will be provided in the SAP, which will be finalized before database lock and treatment unblinding.

#### **9.7.1.1 Study Endpoints**

##### **Co-PRIMARY ENDPOINT(S)**

- 1) Cognitive function: Alzheimer's Disease Assessment Scale-Cognitive Subscale (ADAS-cog)

Assessment of cognitive function measured by ADAS-cog from baseline to Week 24.

- 2) Global function: Clinicians Interview-Based Impression of Change-plus (CIBIC-plus)

Assessment of global function measured by CIBIC-plus at Week 24.

##### **SECONDARY ENDPOINT(S)**

- 1) Mini-Mental Status Examination (MMSE)

Assessment of Mini-Mental Status Examination (MMSE) from baseline to Week 24 compared to placebo.

- 2) Executive function test (Trail making test (K-TMT-e))

Assessment of executive function test from baseline to Week 24 compared to placebo.

##### **EXPLORATORY ENDPOINT(S)**

Not applicable

#### **9.7.1.2 Definitions of Analysis Sets**

The Safety Analysis Set (SAS) is the group of subjects who received at least one dose of study drug and had at least one postdose safety assessment.

The Full Analysis Set (FAS) is the group of randomized subjects who received at least one dose of study drug and had at least one postdose primary efficacy measurement.

The Per Protocol Set (PPS) is the group of subjects who sufficiently complied with the protocol. Details of the evaluability criteria will be determined before database lock and treatment unblinding and will be specified in the Statistical Analysis Plan.

### 9.7.1.3 Subject Disposition

The disposition of all subjects will be summarized. Subject disposition tables will include the number (percent) of subjects who will:

- randomized into each treatment group;
- included in each analysis populations (Safety, FAS, PPS);
- discontinued from the study early, summarized by reason for discontinuation.

The number of subjects screened and the number (percent) who fail screening will also be summarized.

### 9.7.1.4 Demographic and Other Baseline Characteristics

Demographic and other baseline characteristics for each analysis set will be summarized for each treatment group and total of treatment groups using descriptive statistics (e.g., mean, SD, median, minimum, maximum and frequency, proportion). Continuous demographic and baseline variables include age, weight etc. Categorical variables include sex, age group etc.

### 9.7.1.5 Prior and Concomitant Therapy

Prior medication is defined as any medication taken prior to the first dose of study drug. Concomitant medication is defined as any medication taken during the treatment period between the date of the first dose of study drug and the date of the last dose of study drug, inclusive.

Prior medications and concomitant medications will be summarized in number and percentages of subjects by Anatomical Therapeutic Chemical (ATC) Code by treatment group for all subjects.

### 9.7.1.6 Efficacy Analyses

The efficacy data observed from baseline to Week 24 will be used for analysis. All statistical tests will be conducted at the significance level of 5.0% (two-tailed).

The analysis will be conducted on the FAS and PPS, using the last observation carried forward (LOCF) method to impute missing data at Week 24, unless otherwise specified, and the observed cases (OC) populations at Week 24 and other time points.

The analysis of FAS is primary, and that of PPS is a sensitivity analysis of FAS.

## CO-PRIMARY EFFICACY ANALYSIS

The co-primary efficacy variables are used as follows to determine whether donepezil has superior efficacy compared to placebo:

- For ADAS-cog change from baseline to Week 24, an analysis of covariance (ANCOVA) model with baseline as covariates and treatment as main effect will be used for testing main effect.
- For CIBIC-plus scores, least squares (LS) mean scores at Week 24 will be compared between groups to demonstrate numerical superiority of donepezil to placebo (the

difference is less than 0), using ANCOVA model with CIBIS-plus (covariate) and treatment group (main effect).

For the measurements of each visit and the change from baseline to each visit of both endpoints, descriptive statistics (median, mean, SD, minimum, maximum and number of patients with non-missing data for both variables; number and percentages of each score for CIBIC-plus) will be presented. Where appropriate, least square (LS) mean, between-treatment difference in least square (LS) means, 95% confidence intervals (CIs) for the difference and p value in each visit will also be presented.

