#### Primary Efficacy Analyses:

The co-primary efficacy variables are used as follows to determine whether donepezil has superior efficacy compared to placebo:

- For ADAS-cog change from baseline to Week 24, an analysis of covariance (ANCOVA) model with baseline (covariate) and treatment (main effect) will be used for testing main effect.
- For CIBIC-plus scores, least squares (LS) mean scores at Week 24 will be compared between groups to demonstrate numerical superiority of donepezil to placebo (the difference is less than 0), using ANCOVA model with CIBIS-plus (covariate) and treatment group (main effect).

For the measurements of each visit and the change from baseline to each visit of both endpoints, descriptive statistics (median, mean, standard deviation (SD), minimum, maximum, and number of patients with non-missing data for both variable; number and percentages of each score for CIBIC-plus) will be presented. Where appropriate, least square (LS) mean, between-treatment difference in least square (LS) means, 95% confidence intervals (CIs) for the difference and p value in each visit will also be presented.

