#### 9.4.3 Method of Assigning Subjects to Treatment Groups

At the time of the Baseline visit, patients meeting the eligibility criteria will be randomly assigned (1:1) to either donepezil group or placebo group by IWRS system according to a computer-generated randomization code generated by an independent statistician.

The list of patient randomization codes will be generated using PROC PLAN in the SAS® procedures. A stratified block randomization approach will be used for the randomization with MMSE ( $\leq 19$ ,  $20 \leq$ ) as stratum in each study site.

(Open-label extension)

This is an open-label extension phase. Subjects, who have completed the DB phase and have consented to continue participation of the study, can be enrolled in the 24-week open-label extension phase. All subjects who provide signed informed consent to participate in this phase will be assigned to receive active drug. There is no randomization in this phase.

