#### 9.5.1.3 Efficacy Assessments

##### **Primary efficacy variable:**

- 1) Cognitive function: Alzheimer's Disease Assessment Scale-Cognitive Subscale (ADAS-cog)

ADAS-cog will be assessed at Visit 2, 3, 5, 6, and 7 (Week 0, 4, 12, 18, and 24). Every ADAS-cog test for one subject should be administered by one rater throughout the study.

- 2) Global function: Clinicians Interview-Based Impression of Change-plus (CIBIC-plus)

CIBIC-plus will be assessed at Visit 2, 3, 5, and 7 (Week 0, 4, 12 and 24). CIBIS will be assessed at Visit 2 (Week 0). CIBIS and every CIBIC for one subject should be evaluated by one independent rater throughout the study. Clinical information about the subject from any source can be used for the CIBIS, but not at any other time for the CIBIC during the study. The rater will refer to the CIBIS to complete the CIBIC.

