#### **SECONDARY EFFICACY ANALYSES**

MMSE and executive function test score change from Baseline to Week 24 will be analyzed using a same ANCOVA model as is described for the ADAS-cog. Other statistical inference (estimating and testing) will also be analyzed in the same way with primary analysis.

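### Randomisation is stratified by MMSE category within site, but the fixed ANCOVA models leave these factors out, so CIs and p-values are conservative if the factors are prognostic

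*Protocol*

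**What the plan says.** Protocol Section 9.4.3 states: "A stratified block randomization approach will be used for the randomization with MMSE" (≤19, ≥20) "as stratum in each study site". With about 25 sites (Synopsis and Section 6), this gives about 50 site-by-MMSE cells.

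Section 9.7.1.6 fixes the efficacy models:

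- **ADAS-cog change:** "an analysis of covariance (ANCOVA) model with baseline as covariates and treatment as main effect will be used for testing main effect". The Synopsis repeats it: "model with baseline (covariate) and treatment (main effect) will be used for testing main effect".
- **CIBIC-plus at Week 24:** "using ANCOVA model with CIBIS-plus (covariate) and treatment group (main effect"). Success is an LS-mean difference below zero.
- **MMSE and executive function:** change scores "will be analyzed using a same ANCOVA model as is described for the ADAS-cog".
- **Reporting for both co-primaries, where appropriate:** "95% confidence intervals (CIs) for the difference and p value in each visit will also be presented".

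No model contains site. The MMSE stratum is missing from the ADAS-cog, CIBIC-plus and executive-function models. The MMSE model has continuous baseline MMSE as its own covariate, so there only site is unaccounted for. Section 9.7.1 leaves further details to the SAP, but the covariate lists are already stated in the protocol, in two places.

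**The concern.** Blocking within strata forces the arms to be nearly balanced on site and MMSE category. If those factors predict outcome, the balance removes their contribution from the sampling variability of the treatment difference. A model that omits them still counts that contribution as residual noise, so its standard error is larger than the true variability of the estimate. Intervals then over-cover and tests reject less often than their nominal level.

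This costs efficiency and distorts reporting; it does not threaten validity. Two places are affected:

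- **ADAS-cog** is the only co-primary decided by a significance test.
- **CIBIC-plus** is decided by the sign of the difference, so its interval and p-value are what tell a reader whether a global effect is more than noise. Section 7.2 gives inconsistent CIBIC-plus results in earlier trials as the reason for this study.

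**Working it through.** **The plan's own figures (Section 9.7.2).**

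- ADAS-cog, difference 2.404, SD 5.955, 5% two-sided, 80% power: 2 × (1.960 + 0.842)² × (5.955/2.404)² = 96.3, so 97 per arm by the normal formula. The two-sample t test gives 98 per arm (power 80.3%), as stated.
- CIBIC-plus, difference 0.261, SD 1.162, at most a 2.5% chance of the wrong sign: 2 × (1.960 × 1.162/0.261)² = 152.3, so 153 per arm. With the t quantile it is 154, as stated.
- At 154 per arm, ADAS-cog power by t test is 94.2%.

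**Type I error under perfect balance.** Let R² be the share of variance due to site plus MMSE stratum. The true variance of the estimate is (1 − R²) times what the planned model reports, so the type I error is 2 × [1 − Φ(1.96/√(1 − R²))]:

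| R² (assumed) | 2% | 5% | 10% | 15% | 20% |
|---|---|---|---|---|---|
| Type I error | 4.8% | 4.4% | 3.9% | 3.4% | 2.8% |

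**Simulation with incomplete blocks.** From the protocol: 308 analysed patients, 25 sites, and the effects and SDs above. Assumed: blocks of 4, a baseline covariate explaining 5% of variance and correlated 0.6 with MMSE, and the variance shares in the first column. Each scenario had 8,000 null and 4,000 alternative runs. The adjusted model here has site as a fixed effect.

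| Site / MMSE share | Null rejection, planned vs adjusted | ADAS-cog power, planned → adjusted | CIBIC-plus P(difference < 0), planned vs adjusted |
|---|---|---|---|
| 0 / 0 | 0.049 vs 0.051 | 0.946 → 0.941 | 0.976 vs 0.975 |
| 2% / 0 | 0.048 vs 0.052 | 0.958 → 0.956 | 0.975 vs 0.975 |
| 5% / 2% | 0.039 vs 0.047 | 0.958 → 0.963 | 0.983 vs 0.983 |
| 5% / 5% | 0.043 vs 0.054 | 0.960 → 0.968 | 0.983 vs 0.984 |
| 10% / 5% | 0.040 vs 0.054 | 0.961 → 0.975 | 0.989 vs 0.985 |
| 15% / 5% | 0.032 vs 0.051 | 0.968 → 0.982 | 0.988 vs 0.990 |

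**Site as a random intercept (REML), the form proposed below.** 5,000 null and 3,000 alternative runs:

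| Site / MMSE share | Null rejection, planned vs adjusted | ADAS-cog power, planned → adjusted |
|---|---|---|
| 0 / 0 | 0.050 vs 0.051 | 0.952 → 0.949 |
| 2% / 0 | 0.051 vs 0.055 | 0.948 → 0.949 |
| 5% / 5% | 0.041 vs 0.050 | 0.958 → 0.969 |
| 15% / 5% | 0.034 vs 0.053 | 0.963 → 0.978 |

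**CIBIC-plus standard error (site as a fixed effect).** At R² 10% the reported SE falls from 0.128 to 0.123 with adjustment, while the true SE goes only from 0.122 to 0.121. At R² 20% the reported SE falls from 0.128 to 0.115 and the true SE from 0.118 to 0.116. So the planned model overstates the SE by 0.128/0.122 = 1.05 and 0.128/0.118 = 1.08 times. The planned effect is only about two reported SEs (0.261/0.128 = 2.04), so this matters for the nominal p-value. The simulated chance of p < 0.05 goes from 53.0% to 56.2% at 5%/5%, and from 52.6% to 61.1% at 15%/5%. With no prognostic effect it is 53.5% against 53.0%.

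**The case against.** The best case for leaving the models alone is that no planned conclusion is likely to change. CIBIC-plus success depends on a sign, which adjustment moves by at most 0.4 percentage points. ADAS-cog needs 98 per arm and gets 154.

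The ADAS-cog effect is also probably at the low end. The protocol asks that "Every ADAS-cog test for one subject should be administered by one rater throughout the study", so a stable rater or site level partly cancels in the change score, and baseline ADAS-cog plausibly absorbs part of the MMSE stratum effect. In the low-end scenario (site 2%, stratum 0) there is no detectable conservatism and no power gain. Every variance share is an assumption. Whether site is fixed, pooled or random is a choice, and Section 11.1 may require regulatory and ethics submission for a change to the primary model.

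All of this stands as a limit on importance. It does not remove the mismatch or its direction. The low-end argument is weaker for CIBIC-plus, which is itself a rating of change by one rater per subject, so differences in rater severity do not cancel against a baseline score in the same way. Nor can the point be left to the SAP: one that followed the protocol would carry the mismatch forward, and one that added the factors would depart from the protocol's stated models.

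**Conclusion.** The concern holds. The protocol stratifies on two factors and fixes models that omit site throughout and the MMSE stratum everywhere except where continuous baseline MMSE stands in for it. If the factors are prognostic, reported intervals are too wide and p-values too large; if they are not, nothing is lost by the planned models.

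Over an assumed R² of 0 to 20%, simulated type I error of the planned model runs from about 5% to 3.2%. With site as a fixed effect, adjustment changes ADAS-cog power by −0.5 (R² 0), +0.8 (R² 10%) and +1.4 (R² 20%) points. The clearest gain is in the CIBIC-plus interval and p-value. The result rests on assumed variance shares, block length and baseline correlation. It is an inexpensive improvement worth making, not a flaw that endangers the trial's conclusions.

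**What to change.** In Section 9.7.1.6 and the Synopsis:

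- Add the MMSE randomisation stratum (≤19 / ≥20) as a fixed effect and site as a random intercept to the ADAS-cog, CIBIC-plus and executive-function models.
- Add only the site random intercept to the MMSE model.
- Name the degrees-of-freedom method for the mixed model.

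A random intercept avoids a pooling rule for about 50 cells averaging 6 to 7 subjects (308/50 = 6.2 analysed, 324/50 = 6.5 randomised).

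The data are already collected. The statistical cost is one fixed-effect degree of freedom and one variance component, with less than 1 point of ADAS-cog power lost if neither factor is prognostic (95.2% to 94.9%). The administrative cost is a protocol amendment, with whatever review Section 11.1 requires. It should be made before unblinding, because covariates added afterwards would look chosen from the data.
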